17.3.2. LABORATORY REFERENCE RANGES AND ABNORMAL CRITERIA

Quantitative laboratory measurements will be compared with the relevant laboratory reference ranges by the lab vendors and categorized as:

- Low: Below the lower limit of the laboratory reference range
- Normal: Within the laboratory reference range (upper and lower limit included)
- High: Above the upper limit of the laboratory reference range.

Clinical laboratory reference/normal ranges will be listed.

Document: L:\BIOS\Boehringer_Ingelheim_Pharmaceuticals\BI730357\1407-0037_MZA56588\Biostatistics\Documentation\SAP

Author: [REDACTED]

Version Number:

Final V2.0

Version Date:

23JUL2020

Template No: CS_TP_BS016 – Revision 5
Effective Date: 01Apr2018

Reference: CS_WI_BS005

17.4. VITAL SIGNS

The following Vital Signs measurements will be reported for this study:

- Supine Systolic and Diastolic Blood Pressure (mmHg)
- Pulse Rate (bpm)
- Body temperature (°C)
- Weight (kg)
- BMI (kg/m²).

Vital signs will be summarized by treatment using descriptive statistics for baseline, each scheduled visit, and change from baseline to each visit.

Vital signs data will be listed.

17.5. ECG EVALUATIONS

Clinically relevant abnormal findings will be reported either as baseline condition (if identified at the screening visit) or otherwise as AEs and will be followed up and/or treated as medically appropriate.

17.6. PHYSICAL EXAMINATION

The results of physical examination will be only be included in the source documents available at the site.

Document:	L:\BIOS\Boehringer_Ingelheim_Pharmaceuticals\BI730357\1407-0037_MZA56588\Biostatistics\Documentation\SAP		
Author:	██████████	Version Number:	Final V2.0
	Version Date: 23JUL2020		
Template No:	CS_TP_BS016 – Revision 5		
Effective Date:	01Apr2018		
	Reference: CS_WI_BS005		
Copyright © 2009, 2010, 2012, 2016, 2018 █████ All Rights Reserved. The contents of this document are confidential and proprietary to █████ and its subsidiaries. Unauthorized use, disclosure or reproduction is strictly prohibited.			

APPENDIX 1. PROGRAMMING CONVENTIONS FOR OUTPUTS

OUTPUT CONVENTIONS

TABLE AND LISTING OUTPUT CONVENTIONS

General:

The first row in the body of the table or listing should be blank.

The left-hand column should start in column 1. No indenting or centering of the output should occur.

Rounding should be done with the SAS function ROUND, if no further specification.

Numbers in tables should be rounded, not truncated, if no further specification.

Alphanumeric output should be left aligned.

Numbers should be decimal point aligned.

Whole numbers should be right aligned.

Text values should be left aligned.

The first letter of a text entry should be capitalized

Listings of adverse events, concomitant medications, medical histories, etc. should be sorted in chronological order, with earliest adverse event, medication or history coming first.

The trial drug should appear first in tables with treatments as columns.

In general, only present totals (across treatment groups) at baseline/randomization, and do not present them post randomization.

If possible, include 100% frequencies in the table shell, so that it is clear what the denominator is for percentage calculations.

All listing outputs should be sorted (preferably by Treatment, Site Number and Subject Number).

Do not use superscripts and subscripts.

The width of the entire output should match the linesize option.

Univariate Statistics:

Statistics should be presented in the same order across tables (i.e., n, Mean, SD, Median, IQR, Minimum, Maximum or n, gMean, gCV, Mean, CV, SD, Median, Minimum, Maximum).

Document: L:\BIOS\Boehringer_Ingelheim_Pharmaceuticals\BI730357\1407-0037_MZA56588\Biostatistics\Documentation\SAP

Author: [REDACTED] Version Number: Final V2.0
Version Date: 23JUL2020

Template No: CS_TP_BS016 – Revision 5
Effective Date: 01Apr2018

Reference: CS_WI_BS005

Table statistics should line up under the N part of the (N=XXX) in the table header. All decimal points should line up. If the minimum and maximum are output on one line as Minimum, Maximum then the comma should line up with the decimal point.

If the original data has N decimal places, then the summary statistics should have the following decimal places:

- Minimum and maximum: N
- Mean, gMean, median, gCV% and CV%: N + 1
- SD, IQR: N + 2

Frequencies and percentages (n and %):

Percent values should be reported inside parentheses, with one space between the count and the left parenthesis of the percentage. Parentheses should be justified to accept a maximum of 100.0 as a value and padded with blank space if the percentage is less than 100.0. An example is given below:

77 (100.0%)

50 (64.9%)

0 (0.0%)

Percentages will be reported to one decimal place, except percentage <100.0% but >99.9% will be presented as '>99.9%' (e.g., 99.99% is presented as >99.9%); and percentage < 0.1% will be presented as '<0.1%' (e.g., 0.08% is presented as <0.1%). Rounding will be applied after the <0.1% and >99.9% rule.

E.g., (<0.1%)

(6.8%)

(>99.9%)

Percentages may be reported to 0 decimal places as appropriate (for example, where the denominator is relatively small).

Where counts are zero, percentages of 0.0% should appear in the output.

Confidence Intervals:

As a rule, confidence intervals are output to one place more than the raw data, and standard deviations and standard errors to two places more than the raw data.

Confidence intervals should be justified so that parentheses displayed on consecutive lines of a table "line up".

Boundary values of confidence intervals should be separated by a comma.

Boundary values should be padded as necessary to accept negative values and to allow alignment of the decimal place.

Document: L:\BIOS\Boehringer_Ingelheim_Pharmaceuticals\BI730357\1407-0037_MZA56588\Biostatistics\Documentation\SAP

Author: [REDACTED] Version Number: Final V2.0
Version Date: 23JUL2020

Template No: CS_TP_BS016 – Revision 5
Effective Date: 01Apr2018

Reference: CS_WI_BS005

An example is given below:

(-0.12, -0.10)

(9.54, 12.91)

P-values:

P-values should be reported to three decimal places, except values <1.000 but >0.999 will be presented as '0.999' (e.g., 0.9998 is presented as >0.999); and values <0.001 will be presented as '<0.001' (e.g., 0.0009 is presented as <0.001). Rounding will be applied after the <0.001 and >0.999 rule

Ratios:

Ratios should be reported to one more decimal place than the original data.

Spacing:

There must be a minimum of 1 blank space between columns (preferably 2).

Denominators:

If a different count other than the population count is used for a denominator (within the table) to calculate percentages, there should be a row in the table that identifies that number "n".

Alternatively, a footnote should be included in each table with percentages to indicate the denominator for percentages.

Missing values:

A "0" should be used to indicate a zero frequency.

A blank will be used to indicate missing data in an end-of-text table or subject listing.

DATES & TIMES

Depending on data available, dates and times will take the format yyyy-mm-dd; times will take the format hh:mm:ss; combined dates and times will take the format yyyy-mm-ddThh:mm:ss.

SPELLING FORMAT

English US.

PRESENTATION OF TREATMENT GROUPS

For outputs, treatment groups will be represented as follows and in that order:

Document:	L:\BIOS\Boehringer_Ingelheim_Pharmaceuticals\BI730357\1407-0037_MZA56588\Biostatistics\Documentation\SAP		
Author:	██████████	Version Number:	Final V2.0
		Version Date:	23JUL2020
Template No:	CS_TP_BS016 – Revision 5		
Effective Date:	01Apr2018		
	Reference: CS_WI_BS005		

Treatment Group	For Tables and Graphs	For Listings
Placebo QD	Placebo QD	Placebo QD
BI 730357 400 mg QD	BI 730357 400 mg QD	BI 730357 400 mg QD
Placebo BID	Placebo BID	Placebo BID
BI 730357 300 mg BID	BI 730357 300 mg BID	BI 730357 300 mg BID
Ciprofloxacin 500 mg BID	Ciprofloxacin 500 mg BID or Cipro 500 mg BID	Ciprofloxacin 500 mg BID or Cipro 500 mg BID

PRESENTATION OF VISITS

For outputs, visits will be represented as follows and in that order:

Long Name (default)	Short Name
Screening	Scrn
Day -1	
Day x or Day x prodose	Dx or Dx predose
Day x, y hour(s)	Day x, y h
End-of-Treatment	EOT

PRESENTATION OF NOMINAL TIMES

For outputs, nominal times will be represented as follows and in that order:

Long Name (default)	Short Name
x hour(s)	x h

LISTINGS

All listings will be ordered by the following (unless otherwise indicated in the template):

Randomized treatment group [in the order Placebo QD, BI 730357 400 mg QD and ciprofloxacin 500 mg

Document: L:\BIOS\Boehringer_Ingelheim_Pharmaceuticals\BI730357\1407-0037_MZA56588\Biostatistics\Documentation\SAP

Author: [REDACTED] Version Number: Final V2.0
Version Date: 23JUL2020

Template No: CS_TP_BS016 – Revision 5

Reference: CS_WI_BS005

Effective Date: 01Apr2018

BID for the 400 mg QD dose group first and then, Placebo BID and BI 730357 300 mg BID for the 300 mg BID dose group]

subject ID,

date (where applicable),

For listings where non-randomized subjects are included, these will appear in a category after the randomized treatment groups labelled 'Not Randomized'.

The visit as recorded in the eCRF will be displayed in the listings (and not the remapped visit).

Document: L:\BIOS\Boehringer_Ingelheim_Pharmaceuticals\BI730357\1407-0037_MZA56588\Biostatistics\Documentation\SAP

Author:  Version Number: Final V2.0
Version Date: 23JUL2020

Template No: CS_TP_BS016 – Revision 5
Effective Date: 01Apr2018

Reference: CS_WI_BS005

APPENDIX 2. PARTIAL DATE CONVENTIONS

Imputed dates will NOT be presented in the listings.

ALGORITHM FOR TREATMENT EMERGENCE OF ADVERSE EVENTS:

START DATE	STOP DATE	ACTION
Known	Known	If start date < study med start date, then not TEAE If start date >= study med start date, then TEAE
	Partial	If start date < study med start date, then not TEAE If start date >= study med start date, then TEAE
	Missing	If start date < study med start date, then not TEAE If start date >= study med start date, then TEAE
Partial, but known components show that it cannot be on or after study med start date	Known	Not TEAE
	Partial	Not TEAE
	Missing	Not TEAE
Partial, could be on or after study med start date	Known	If stop date < study med start date, then not TEAE If stop date >= study med start date, then TEAE
	Partial	Impute stop date as latest possible date (i.e. last day of month if day unknown or 31st December if day and month are unknown), then: If stop date < study med start date, then not TEAE If stop date >= study med start date, then TEAE
	Missing	Assumed TEAE

Document: L:\BIOS\Boehringer_Ingelheim_Pharmaceuticals\BI730357\1407-0037_MZA56588\Biostatistics\Documentation\SAP

Author: [REDACTED]

Version Number:

Final V2.0

Version Date:

23JUL2020

Template No: CS_TP_BS016 – Revision 5
Effective Date: 01Apr2018

Reference: CS_WI_BS005

START DATE	STOP DATE	ACTION
Missing	Known	If stop date < study med start date, then not TEAE If stop date >= study med start date, then TEAE
	Partial	Impute stop date as latest possible date (i.e. last day of month if day unknown or 31st December if day and month are unknown), then: If stop date < study med start date, then not TEAE If stop date >= study med start date, then TEAE
	Missing	Assumed TEAE

ALGORITHM FOR PRIOR / CONCOMITANT MEDICATIONS:

START DATE	STOP DATE	ACTION
Known	Known	If stop date < study med start date, assign as prior If stop date >= study med start date and start date <= end of treatment, assign as concomitant If stop date >= study med start date and start date > end of treatment, assign as post study
	Partial	Impute stop date as latest possible date (i.e. last day of month if day unknown or 31 st December if day and month are unknown), then: If stop date < study med start date, assign as prior If stop date >= study med start date and start date <= end of treatment, assign as concomitant If stop date >= study med start date and start date > end of treatment, assign as post treatment
	Missing	If stop date is missing could never be assumed a prior medication If start date <= end of treatment, assign as concomitant If start date > end of treatment, assign as post treatment

Document: L:\BIOS\Boehringer_Ingelheim_Pharmaceuticals\BI730357\1407-0037_MZA56588\Biostatistics\Documentation\SAP

Author: [REDACTED]

Version Number:

Final V2.0

Version Date:

23JUL2020

Template No: CS_TP_BS016 – Revision 5
Effective Date: 01Apr2018

Reference: CS_WI_BS005

START DATE	STOP DATE	ACTION
Partial	Known	Impute start date as earliest possible date (i.e. first day of month if day unknown or 1 st January if day and month are unknown), then: If stop date < study med start date, assign as prior If stop date >= study med start date and start date <= end of treatment, assign as concomitant If stop date >= study med start date and start date > end of treatment, assign as post treatment
	Partial	Impute start date as earliest possible date (i.e. first day of month if day unknown or 1 st January if day and month are unknown) and impute stop date as latest possible date (i.e. last day of month if day unknown or 31 st December if day and month are unknown), then: If stop date < study med start date, assign as prior If stop date >= study med start date and start date <= end of treatment, assign as concomitant If stop date >= study med start date and start date > end of treatment, assign as post treatment
	Missing	Impute start date as earliest possible date (i.e. first day of month if day unknown or 1 st January if day and month are unknown), then: If stop date is missing could never be assumed a prior medication If start date <= end of treatment, assign as concomitant If start date > end of treatment, assign as post treatment
Missing	Known	If stop date < study med start date, assign as prior If stop date >= study med start date, assign as concomitant Cannot be assigned as 'post treatment'
	Partial	Impute stop date as latest possible date (i.e. last day of month if day unknown or 31 st December if day and month are unknown), then: If stop date < study med start date, assign as prior If stop date >= study med start date, assign as concomitant Cannot be assigned as 'post treatment'
	Missing	Assign as concomitant

Document: L:\BIOS\Boehringer_Ingelheim_Pharmaceuticals\BI730357\1407-0037_MZA56588\Biostatistics\Documentation\SAP

Author: [REDACTED]

Version Number:

Final V2.0

Version Date:

23JUL2020

Template No: CS_TP_BS016 – Revision 5
Effective Date: 01Apr2018

Reference: CS_WI_BS005

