7.2.5 Safety analyses

Adverse events will be coded using the Medical Dictionary for Drug Regulatory Activities (MedDRA). Standard BI summary tables and listings will be produced. All adverse events with an onset between start of treatment and end of the REP, a period of 7 days after the last dose of trial medication, will be assigned to the on-treatment period for evaluation.

The safety analysis will be done by 'randomised treatment'.

All treated subjects will be included in the safety analysis. In general, safety analyses will be descriptive in nature and will be based on BI standards. No hypothesis testing is planned.

Statistical analysis and reporting of adverse events will concentrate on treatment-emergent adverse events, i.e. all adverse events occurring between start of treatment and end of the REP. Adverse events that start before first drug intake and deteriorate under treatment will also be considered as 'treatment-emergent'.

Frequency, severity, and causal relationship of adverse events will be tabulated by system organ class and preferred term after coding according to the current version of the Medical Dictionary for Drug Regulatory Activities (MedDRA) at database lock.

c27983101-03 Clinical Trial Protocol Page 66 of 79

Proprietary confidential information © 2020 Boehringer Ingelheim International GmbH or one or more of its affiliated companies

Laboratory data will be analysed both quantitatively as well as qualitatively. The latter will be done via comparison of laboratory data to their reference ranges. Values outside the reference range as well as values defined as clinically relevant will be summarised. Treatment groups will be compared descriptively with regard to distribution parameters as well as with regard to frequency and percentage of subjects with abnormal values or clinically relevant abnormal values.

Vital signs, physical examinations, or other safety-relevant data observed at screening, baseline, during the course of the trial and at the end-of-trial evaluation will be assessed with regard to possible changes compared to findings before start of treatment.

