17.1. ADVERSE EVENTS

An AE is defined as any untoward medical occurrence in a patient or clinical investigation subject administered a medicinal product and which does not necessarily have to have a causal relationship with this treatment. An AE can therefore be any unfavorable and unintended sign (including an abnormal laboratory finding), symptom, or disease temporally associated with the use of a medicinal product, whether or not considered related to the medicinal product.

Protocol-specified Adverse Events of Special Interest (AESI) and infection AEs are identified on the eCRF by the investigator.

All adverse events with an onset between start of study medication and 7 days after the last dose study medication (i.e., end of the residual effect period [REP]) will be assigned to the on-treatment period for evaluation and considered as on-treatment AEs. Only on treatment AEs are considered for the summary of adverse events. Adverse Events (AEs) will be coded using MedDRA.

Treatment-emergent adverse events (TEAEs) are defined as AEs occurring between start of study medication and 7 days after the last dose study medication (i.e., end of the REP) inclusive. Adverse events that start before first study medication intake and deteriorate under treatment will also be considered as 'treatment-emergent'.

Pretreatment AEs are defined as AEs occurring prior to dosing. These events will be presented in the listings only and are not included in the tabular summary of AEs.

See APPENDIX 2 for handling of partial dates for AEs. In the rare case where it is not possible to assess treatment emergence, the AE will be classified as treatment emergent (i.e. the worst case).

Intensity (Severity)

The AE intensity is classified as mild/moderate/severe. TEAEs starting after the first dose of study medication with a missing severity will be classified as severe for analysis purposes. If a subject reports a TEAE more than once within that system organ class (SOC)/preferred term (PT), the AE with the worst case severity will be used in the corresponding severity summaries.

Causal Relationship to Study Medication

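### SAP Appendix 2 classes an adverse event known to start before first dose as not treatment-emergent even if it worsens on drug, contrary to SAP 17.1 and protocol 7.2.5

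*SAP*

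**What the plan says.** The definition in the body of both documents includes worsening. Protocol 7.2.5: "Adverse events that start before first drug intake and deteriorate under treatment will also be considered" as treatment-emergent. SAP 17.1 repeats the rule almost word for word: "Adverse events that start before first study medication intake and deteriorate under treatment will also be considered" as treatment-emergent. Both end the window at the close of the 7-day residual effect period.

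SAP Appendix 2 then gives an algorithm for treatment emergence, laid out by start date and stop date:

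- Known start, with a known, partial or missing stop: "If start date < study med start date, then not TEAE"; otherwise "If start date >= study med start date, then TEAE".
- Start described as "Partial, but known components show that it cannot be on or after study med start date": not TEAE in all three stop-date rows.
- Ambiguous partial start, or missing start: decided by the stop date. Where a stop date can be used, "If stop date >= study med start date, then TEAE"; where the stop date is missing, the event is assumed to be a TEAE.

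SAP 17.1 also says that only on-treatment events, defined by onset, enter the summaries, and that events occurring before dosing are listed but not tabulated. It refers to Appendix 2 for partial dates. Neither place says which governs if the two differ.

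**The concern.** A programmer deriving the TEAE flag has two rules that give different answers for the same record. The one set out as a decision table leaves out a class of events that the protocol says must be counted. If the flag follows Appendix 2, a pre-dose event that gets worse on BI 730357, placebo or ciprofloxacin moves from the incidence tables to a listing, and the tables no longer match the protocol's definition of treatment emergence.

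Such events can be recorded in this trial. Adverse events are collected from informed consent (protocol 5.2.6.2.1), and screening may begin up to 28 days before dosing.

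**Working it through.** The plan gives no figure to reproduce, so the check compares the two rules case by case.

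Inputs, on planned protocol days: Part A is dosed from Day 1 to Day 8, Part B from Day 3 to Day 8 (protocol 3.1). The residual effect period is 7 days (protocol 1.2), so the window closes on Day 8 + 7 = Day 15. Screening can start on Day -28.

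Rules for a known start date:

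- Appendix 2: TEAE if start ≥ first dose.
- SAP 17.1: TEAE if first dose ≤ start ≤ last dose + 7 days, or if start < first dose and the event worsens under treatment.

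| Start of event | SAP 17.1 | Appendix 2 | Agree? |
|---|---|---|---|
| Before first dose, no worsening | Not TEAE | Not TEAE | Yes |
| Before first dose, worsens on treatment (Part A Days -28 to -1; Part B Days -28 to 2) | TEAE | Not TEAE | **No** |
| First dose to Day 15 | TEAE | TEAE | Yes |
| Day 16 onward | Not TEAE | TEAE | **No** |

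Applying both rules to every start day from -28 to 30, with and without worsening, gives disagreement in those two regions and nowhere else.

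A partial start that must precede first dose follows the second row of the table: Appendix 2 again has no worsening branch. Ambiguous and missing starts do not share the problem, because the stop date decides them and they can become TEAEs. This produces an odd ordering. An event with no start date that stops after first dose is a TEAE, while an event with a documented pre-dose start and documented worsening on drug is not. Better data yield the less cautious classification, although 17.1 says that events which cannot be assessed are to be taken as treatment-emergent.

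Correcting Appendix 2 alone would not be enough. The 17.1 sentences that limit the summaries to events with onset on treatment, and that send pre-dose events to listings only, could still keep a worsened pre-dose event out of the tables.

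Weight of one event, using the planned group sizes in protocol 3.2 and the columns in SAP section 17:

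- BI 730357, one dose group: 1/27 = 3.7%
- BI 730357 pooled: 1/54 = 1.9%
- Placebo pooled: 1/18 = 5.6%
- Ciprofloxacin: 1/12 = 8.3%

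The table of non-serious TEAEs shows preferred terms above 5% in at least one group. One event in the ciprofloxacin or pooled placebo column is therefore enough to decide whether a term appears. These figures show what one event weighs; they do not estimate how many there will be.

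**The case against.** The best defence is that Appendix 2 is headed as a set of partial-date conventions and that 17.1 refers to it only for partial dates, so the definition in 17.1 governs complete dates. This has some force: it makes the omission a risk rather than a certainty. It does not remove the conflict. The first row of the table covers a known start with a known stop, the table is titled as the algorithm for treatment emergence, and no precedence is stated.

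Several stronger readings are tempting, and the documents do not support them.

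- *Skin reactions.* Subjects are irradiated on Days -3, -2 and -1, so a reader might infer that worsening irradiation-site reactions, and with them the trial's main safety signal, would be lost. On-drug photosensitivity is tested by a new irradiation on Day 8, on naive skin sites, and scored on separate scales (protocol 5.1). If a reaction to that irradiation is recorded as an adverse event, it starts after first dose and is a TEAE under either rule. No text says that baseline-site reactions are recorded as adverse events, or whether worsening is entered as a new event with its own onset date.
- *Imbalance between arms.* The ciprofloxacin pre-dose period is two planned days longer, which might suggest bias. Those days have no irradiation, BI 730357 and placebo share one pre-dose schedule, and the safety analysis is descriptive.
- *Missing upper limit.* The second region of disagreement is real but has little effect. CRF collection of adverse events ends at the End of Trial visit (protocol 5.2.6.2.1), which is 7 days after last intake (protocol 6.2.3). It matters mainly if that visit is late.

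**Conclusion.** The contradiction is in the text and should be resolved before database lock. Appendix 2 classes an event whose start is known, or shown by its partial date, to precede first dose as not treatment-emergent, with no exception for worsening. SAP 17.1 and protocol 7.2.5 require the opposite when the event deteriorates on treatment. The consequence is limited to the adverse event tables: affected events would still be listed, and the photosensitivity index, MED and skin-reaction analyses do not change.

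The size in events is unknown. An effect on the tables rests on two assumptions: that the flag is coded from Appendix 2, and that a worsening event keeps its pre-dose onset date in the database. If the site enters worsening as a new event dated on or after first dose, Appendix 2 already classes it as a TEAE.

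**What to change.** 1. In Appendix 2, in the three known-start rows and the three rows for partial starts that must precede first dose, add: unless the AE deteriorates on or after first dose, in which case TEAE.
2. State how deterioration is identified from the eCRF: which field shows it, and whether worsening is a new record or an update to the existing one. The documents do not define it, so the sponsor should.
3. In SAP 17.1, amend the sentences on on-treatment and pretreatment events so that pre-dose events that worsen on treatment enter the summaries as well as the listings.
4. As a minor alignment, add a condition that the start date is no later than last dose date + 7 days, for known-start TEAE conditions only. It cannot be evaluated when the start is missing, so missing and ambiguous starts should keep their present worst-case handling.

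The cost is a few lines of SAP text, one derived flag and a check of the eCRF specification. No data collection beyond the existing eCRF is needed if it already records worsening; if it does not, that should be settled before lock.
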